5.6.3. HHD Megascore

General Description

Twenty-two muscles in 11 pairs are examined in both upper and lower extremities (left and right shoulder flexion, left and right elbow flexion, left and right elbow extension, left and right wrist extension, left and right abduction index finger, left and right abduction thumb, left and right abduction 5th digit, left and right hip flexion, left and right knee flexion, left and right knee extension, left and right ankle dorsiflexion).

Each muscle is tested at least twice. If the difference between the first two trials is greater than 15%, or if the evaluator thinks that one of the first two trials was not valid, a third trial may be performed. The maximum value of the two highest measures within 15% variability will be used for the analysis. If there is no pair with $\leq 15\%$ variability, then the maximum value of the two values that are closest together will be used for the analysis.

CONFIDENTIAL

The information contained herein may not be used, disclosed, or published without the written consent of
Biogen MA Inc.

5.6.4. Percent Predicted SVC

General Description

Vital capacity will be measured by means of the slow vital capacity (SVC) test using a facemask with the participant sitting upright. SVC will be determined by performing at least 3 trials. If the difference between the two highest values of the three trials is $\geq 10\%$, then up to 5 trials may be performed. The maximum percent predicted SVC value at each visit will be used for the analysis.

CONFIDENTIAL

The information contained herein may not be used, disclosed, or published without the written consent of
Biogen MA Inc.

A large black rectangular redaction box covers the majority of the page content, starting below the header and ending above the footer. It is positioned in the center of the page.

The image consists of a series of horizontal black bars of varying lengths and positions, set against a white background. The bars are irregular in shape, with some having sharp ends and others being more rounded. They are positioned at different heights and widths, creating a sense of depth and complexity. The overall effect is reminiscent of a digital signal or a heavily processed image.

CONFIDENTIAL

CONFIDENTIAL
The information contained herein may not be used, disclosed, or published without the written consent of Biogen MA Inc.

CONFIDENTIAL

CONFIDENTIAL

A high-contrast, black and white image showing a series of horizontal bars of varying lengths. The bars are mostly black, set against a white background. The lengths of the bars decrease from top to bottom. The image is heavily processed, appearing as a binary black and white pattern.

5.7. Safety Endpoints

The safety population will be used for the analyses of the safety data. Safety data will be summarized using descriptive statistics by dose level or cohort.

All adverse events (AEs) and serious adverse events (SAEs), clinical laboratory data, vital sign measurements, neurological exams, ECG readings, and CSSRS will be evaluated for safety. Safety data will be summarized using descriptive statistics.

CONFIDENTIAL

CONFIDENTIAL
The information contained herein may not be used, disclosed, or published without the written consent of
Biogen MA Inc.

Safety data will be summarized by dose level and treatment assignments (BIIB105 5 mg [Cohort A], 20 mg [Cohort B], 60 mg [Cohorts C1+ C2], 120 mg [Cohorts D1+D2], Pooled Placebo 1+2. Selected safety data will also be summarized by cohort and treatment assignment in Part 1 (BIIB105-treated Cohorts A, B, C1, C2, D1, and D2; Pooled Placebo 1 and Pooled Placebo 2).

5.7.1. Adverse Events

All AEs will be classified using MedDRA version 26.1 or later if available. Only treatment emergent AEs (TEAEs) will be summarized, where treatment emergence will be relative to the first dose of study drug. A treatment emergent AE/SAE is defined as any AE/SAE with an onset date that is on or after the first dose of study drug or any pre-existing condition that has worsened in severity after the first dose of study drug. Whenever possible, date/time will be used to determine whether an event is treatment emergent. If an event date (start or end) is incomplete, a TEAE will be determined assuming most conservative way as follows:

- If onset day is missing and the month and year are the same as or after the treatment start date, then that event is considered treatment emergent.
- If both onset month and day are missing and the year is the same as or after the treatment start date, then that event is considered treatment emergent.
- If both onset date and end date are completely missing, an event will be considered as a TEAE.
- If onset date is completely missing and end date is not missing which is after the first dose of study drug, an event will be considered as a TEAE.

The incidence of TEAEs will be summarized by dose level (or cohort) and overall BIIB105 as follows:

- Overall summary of TEAE
- TEAEs by primary SOC and MedDRA preferred term
- TEAEs by MedDRA preferred term
- SAEs by primary SOC and MedDRA preferred term
- SAEs by MedDRA preferred term
- Related SAEs by primary SOC and MedDRA preferred term
- TEAEs by CTCAE grading, primary SOC and MedDRA preferred term
- TEAEs with severity greater than or equal to 3 by primary SOC and MedDRA preferred term
- Related TEAEs by primary SOC and MedDRA preferred term
- TEAEs that led to discontinuation of study treatment by primary SOC and MedDRA preferred term
- TEAEs that led to study drug interruption by primary SOC and MedDRA preferred term

CONFIDENTIAL

The information contained herein may not be used, disclosed, or published without the written consent of Biogen MA Inc.

- TEAEs that led to withdrawal from study by primary SOC and MedDRA preferred term
- TEAEs related to the lumbar puncture by primary SOC and MedDRA preferred term
- TEAEs that led to death by primary SOC and MedDRA preferred term
- TEAEs within 24 hours of dosing by primary SOC and MedDRA preferred term

Due to the different durations of exposure to BIIB105 and washout periods for some participants, exposure-adjusted incidence rates will be summarized. Follow-up adjusted incidence rates will also be summarized.

For the summary of TEAEs by severity, primary system organ class and/or preferred term, participants will be counted only once within each primary SOC/MedDRA preferred term and will only be counted under the maximum severity.

For the summary of TEAEs by relationship to study treatment, a subject will be counted only once and in the category of the strongest relationship to study treatment within each SOC/preferred term. The relationship to study treatment will be classified as related or not related.

Listings of all AEs, SAEs, AEs that led to study drug discontinuations, AEs that led to study withdrawals, and AEs that led to study rug interruption will be presented. Listing of death will be provided.

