3.2. Study Treatment

Participants with ALS:

Cohort A: BIIB105 5 mg or placebo

Cohort B: BIIB105 20 mg or placebo

Cohort C1: BIIB105 60 mg or placebo

CONFIDENTIAL

The information contained herein may not be used, disclosed, or published without the written consent of Biogen MA Inc.

Cohort D1: BIIB105 120 mg or placebo

Participants with polyQ-ALS:

Cohort C2: BIIB105 60 mg or placebo

Cohort D2: BIIB105 120 mg or placebo

Participants in Cohorts A, B, C1, and C2 will receive 3 loading doses administered every 2 weeks (on Days 1, 15, and 29), followed by 2 maintenance doses administered once every 4 weeks (on Days 57 and 85), for a total of 5 doses over approximately 13 weeks.

Participants in Cohorts D1 and D2 will receive 3 loading doses administered every 2 weeks (on Days 1, 15, and 29), followed by 5 maintenance doses administered once every 4 weeks (on Days 57, 85, 113, 141, and 169), for a total of 8 doses over approximately 25 weeks.

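### The Part 1 table of TEAEs within 24 hours of dosing counts participants across up to 5 doses in Cohorts A to C2 and up to 8 in D1 and D2, so dose level is confounded with the number of at-risk windows

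*SAP*

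**What the plan says.** Part 1 SAP 5.7.1 introduces its list of AE tables with "The incidence of TEAEs will be summarized by dose level (or cohort) and overall BIIB105 as follows", and one entry is "TEAEs within 24 hours of dosing by primary SOC and MedDRA preferred term". For summaries by severity, SOC and/or preferred term, the same section says that "participants will be counted only once within each primary SOC/MedDRA preferred term". No count per administration is described.

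Part 1 SAP 3.2 gives the schedules. Cohorts A, B, C1 and C2 are dosed on Days 1, 15, 29, 57 and 85, "for a total of 5 doses over approximately 13 weeks". Cohorts D1 and D2 are dosed on those days and on Days 113, 141 and 169, "for a total of 8 doses over approximately 25 weeks". Section 2.2 words both totals as maxima.

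Part 1 SAP 5.7 shows 5, 20 and 60 mg (all five-dose cohorts) beside "120 mg [Cohorts D1+D2], Pooled Placebo 1+2". Selected safety data are also shown by cohort, with the two placebo pools separate.

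On unequal observation, 5.7.1 states: "Due to the different durations of exposure to BIIB105 and washout periods for some participants, exposure-adjusted incidence rates will be summarized". It then adds follow-up-adjusted rates. It does not say which tables receive either rate, and it does not define the denominators. Section 5.5 defines duration of exposure as last dose date minus first dose date plus 1.

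**The concern.** Most AE tables accrue over calendar time. This one accrues only in the 24 hours after each injection, so the opportunity to be counted is set by the number of doses. That number is fixed by cohort and tracks dose level exactly: every 5, 20 and 60 mg participant is scheduled for five windows and every 120 mg participant for eight. A multiple-ascending-dose safety table is read for dose response, and here a step at the top dose is built in whether or not the drug has an acute effect. The table bears on acute tolerability of the intrathecal injection, which is part of the Part 1 primary objective. A spurious step could be read as dose-limiting, or a real one could be dismissed as an artefact.

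**Working it through.** **Inputs**

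- Doses per participant: 5 (A, B, C1, C2) and 8 (D1, D2), from Part 1 SAP 3.2. Counting the listed days reproduces both totals.
- Planned sizes, from Protocol 5.3.1: 6 active at 5 mg, 6 at 20 mg, 9 + 3 = 12 at 60 mg, and 36 + 12 = 48 at 120 mg. Placebo is 2 + 2 + 3 + 1 = 8 on five doses and 12 + 6 = 18 on eight, 26 in all. Placebo in A, B, C1 and D1 sums to 2 + 2 + 3 + 12 = 19, as SAP 2.3 states.
- Risk *p* of a TEAE within 24 hours of one dose: not given. Assumed equal in every arm and shown over a range. Doses are taken as independent and all given.

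**Share ever affected**

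Five doses: 1 − (1 − p)^5. Eight doses: 1 − (1 − p)^8. Pooled placebo: (8 × five-dose value + 18 × eight-dose value) / 26.

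At p = 5%: 1 − 0.95^5 = 22.6%; 1 − 0.95^8 = 33.7%; placebo (8 × 22.6 + 18 × 33.7) / 26 = 30.3%.

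| p | 5/20/60 mg | 120 mg | Pooled placebo | 120 minus 60 mg | 120 mg minus placebo | 60 mg minus placebo |
|---|---|---|---|---|---|---|
| 2% | 9.6% | 14.9% | 13.3% | +5.3 | +1.6 | −3.7 |
| 5% | 22.6% | 33.7% | 30.3% | +11.0 | +3.4 | −7.6 |
| 10% | 41.0% | 57.0% | 52.0% | +16.0 | +4.9 | −11.1 |
| 20% | 67.2% | 83.2% | 78.3% | +16.0 | +4.9 | −11.1 |

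**Largest possible gap.** With q = 1 − p, q^5 − q^8 peaks at q^3 = 5/8, that is p of about 14.5%, where it equals 17.1 points. The gap against pooled placebo is 8/26 of this for 120 mg (5.3 points) and 18/26 for 60 mg (11.9 points, below placebo).

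**Within-participant correlation.** A beta-binomial with mean p = 5% gives an excess over 60 mg of 4.9 points at correlation 0.2 and 1.9 at correlation 0.5. Against pooled placebo the figures are 1.5 and 0.6. If all events followed Dose 1, the gap would be zero.

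**Planned adjustments, p = 5%**

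- Follow-up time to the Week 25 visit is about 175 days (A to C2) against 176 (D1, D2). The 120 mg to 60 mg ratio is 1.49 crude and 1.48 adjusted, so the excess stays. D1 and D2 participants who do not enter Part 2 are followed to Day 259. Their adjusted rate would fall for a reason unrelated to acute risk.
- Exposure time under Section 5.5 is 85 against 169 days on the nominal schedule. Injections per exposure day are 5/85 = 0.0588 and 8/169 = 0.0473, which is 1.24 times as many in A to C2. Affected participants per person-year would be 0.972 at 60 mg and 0.727 at 120 mg, a ratio of 0.75. With time censored at the first event the ratio is 0.81. Either way the adjustment over-corrects.

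**After the fix.** The expected per-administration proportion is 5.0% in every group. Restricted to the five shared dosing days, participant incidence is 22.6% in every group. Both ratios are 1.00.

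**The case against.** The table is descriptive and carries no test. The Part 1 primary endpoint is overall AE and SAE incidence, of which this is one listing entry. It is not the only view of acute tolerability: lumbar-puncture-related TEAEs have their own table, and there each cohort type has about eight CSF collections (Days 1, 15, 29, 57, 85, 92, 130 and 175 in A to C2; the eight dosing days in D1 and D2 participants who enter Part 2). Dosing and AE listings would let a reader build per-dose counts.

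The comparison with control is little affected. Of 26 placebo participants, 18 also have eight windows, and the 3.4-point excess at p = 5% sits beside a sampling standard error of about 11 points. The 60 mg deficit of 7.6 points is 0.9 of a person among 12. If this table is among those shown by cohort, D2 against Pooled Placebo 2 (six of seven on eight doses) would differ by only 11.0 × 1/7 = 1.6 points at p = 5%.

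All of this stands, and it limits the size and importance of the point. It does not remove the confounding in the dose-level display. The lumbar-puncture table depends on attribution and is not confined to 24 hours. The by-cohort view is promised only for selected data, and it still leaves D1 against Pooled Placebo 1 (7 of 19 on five doses) 11.0 × 7/19 = 4.1 points apart.

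A reader might go further and infer that the SAP's exposure adjustment will reverse the error in this table. The documents do not support that as a firm statement. Section 5.7.1 attaches no adjusted rate to this table and defines no denominator, so the over-correction is conditional on using the Section 5.5 definition. Adding an assumed 28 days after the last dose gives (5/113) / (8/197) = 1.09 instead of 1.24. Exposure is also not the only adjustment planned, and the follow-up-adjusted rate does not reverse anything.

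**Conclusion.** The point holds as a weakness of one descriptive table. Under equal per-dose risk its dose-level display shows more affected participants at 120 mg than at 5, 20 or 60 mg. The gap is 11.0 points at an assumed 5% per dose and at most 17 at any risk. It also shows 60 mg below pooled placebo by up to about 12 points. The direction follows from the SAP's own dosing days and does not depend on the assumed risk. The size rests on independent doses and full dosing, and correlation, early discontinuation or clustering at Dose 1 would reduce it.

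A reader might infer a material false signal for 120 mg against placebo. That is not supported: the excess there is at most 5.3 points. Nor is the Part 1 primary endpoint as a whole put in doubt. The two planned rate adjustments do not solve the problem, because neither uses the number of doses as its denominator.

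**What to change.** In Part 1 SAP 5.7.1, for this table only:

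- Add the number of doses followed by at least one TEAE within 24 hours, divided by doses given, by dose level and for placebo. Note that doses within a participant are correlated, so a simple binomial standard error would be wrong.
- Add participant incidence restricted to Doses 1 to 5 (Days 1, 15, 29, 57 and 85), which all cohorts share. This is needed as well: if risk is concentrated at the first dose, the per-administration figure is diluted over eight doses at 120 mg and five elsewhere.
- State that neither exposure days nor follow-up time is used as this table's denominator.

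The cost is SAP wording, one extra denominator from the dosing CRF and one further display. No new data are needed, and the planned participant-incidence table can stay beside the additions.

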5.7.2. Laboratory Data

Laboratory data will be evaluated to determine the incidence of abnormalities that emerge during the study. Changes in laboratory evaluations will be presented relative to baseline, which is defined as the closest visit prior to the subject start treatment. Baseline value is defined as data collected which are prior to and/or on the date of the first dose, usually also the same day as the Day 1 visit. If there is more than one value on or before Day 1, then the last non-missing value prior to (including on) the date of first dose will be used as the baseline value.

The following clinical laboratory parameters are assessed in the protocol:

- Hematology panel: complete blood count with differential
- Blood chemistry panel: total protein, albumin, HbA1c, lipid panel, creatinine, blood urea nitrogen, uric acid, bilirubin (total and direct), alkaline phosphatase, alanine aminotransferase, aspartate aminotransferase, gamma-glutamyl transferase, glucose, calcium, phosphorus, bicarbonate, chloride, sodium, and potassium
- Urinalysis: Dipstick for blood, protein, and glucose (microscopic examination, if abnormal)
- CSF analysis: red blood cell count, white blood cell count, protein, and glucose.
- Coagulation: PT (prothrombin time), aPTT (activated partial thromboplastin time), and INR (international normalized ratio).

CONFIDENTIAL

The information contained herein may not be used, disclosed, or published without the written consent of Biogen MA Inc.

Shift analyses

Each hematology, blood chemistry, coagulation and CSF laboratory parameter will be flagged as “low” or “high” relative to the parameter’s normal range or as “unknown” if no results is available. All visits with available results, including unscheduled visits, will be included in shift analysis.

For each urinalysis laboratory parameter, the number and percentage of participants experiencing post-dosing shifts to abnormal will be summarized.

For each hematology, blood chemistry, coagulation and CSF laboratory, the number and percentage of participants experiencing post-dosing shifts to “low” or “high” will be summarized. Shift to low includes results from normal to low, high to low, and unknown to low. Shift to high includes results from normal to high, low to high, and unknown to high. In each summary, the denominator for the percentage is the number of participants at risk for the shift. The number at risk for the shift to low is the number of participants whose baseline values is not low and who have at least one post-baseline value. The number at risk for the shift to high is the number of participants whose baseline value is not high and who have at least one post-baseline value. A participant will be counted only once for each parameter and each type of shift if there are more than one occurrence for that parameter and that type of shift among post-dosing assessments. Participants with shift will be listed by laboratory parameter and shift type.

Summary of change from baseline and other analysis

In addition to the shift analysis, descriptive statistics (N, mean, SD, median, 1st and 3rd quartiles, and minimum and maximum values) for observed laboratory values, change from baseline and percentage change from baseline in laboratory values of hematology, blood chemistry, and coagulation will be summarized by treatment group and visit. Line plots showing mean and change from baseline value for each treatment over visits will also be presented. Only scheduled visits will be included in these summaries. Spaghetti plots by site will be presented for CSF samples. Proportion of participants with CSF WBC values above 5, 10, and 20 10⁶/L and proportion of participants with CSF protein level above 4X, 3X, and 2X ULN (upper limit of normal) will be summarized.

Listing of all chemistry, hematology, coagulation, CSF, and urinalysis values will be provided. Abnormal values will be flagged.

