13.3.1.2. Laboratory Results

Laboratory data includes hematology, coagulation, blood chemistry, CSF assessments, and urinalysis, and will be summarized. Summary statistics for actual values and changes from baseline will be presented for quantitative laboratory data. In addition, shift tables will be used to tabulate the shifts from baseline to high/low status for each laboratory test.

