15.1.5. Central Laboratories for Laboratory Assessments

A central laboratory has been selected by the Sponsor to analyze all hematology, coagulation testing, blood chemistry, and urine samples collected for this study, except for urine pregnancy tests and CSF, which will be analyzed by a local laboratory; repeat coagulation test will be analyzed by either the local laboratory or the central laboratory. A central laboratory will be utilized to test/confirm polyQ status for participation in Cohorts C2 and D2.

PK samples will be analyzed at a laboratory selected by the Sponsor. Duplicate PK samples will be collected in case the original sample is lost, damaged, or not evaluable.

The central laboratory will also receive, track, and ship all blood samples for specialized
genotyping, PK and PD biomarker analysis,
, and CSF samples for PK and PD biomarker analysis, including aliquots from these
samples, retained as backup in case original samples are lost or not evaluable. Residual blood
samples for future DNA testing will be processed to purify DNA and stored by the central
laboratory.
J

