Participants Included	Total of all participants in Part 1 Cohorts D1 and D2 exposed to BIIB105 120 mg during either Part 1 (i.e. DL1) or initiated during Part 2 (DL2); regardless of whether they entered Part 2. Note a subset of tables will be presented for DL1 and DL2.	All participants who received at least one dose of BIIB105 60 mg in either Part 1 or Part 2.	All participants who received at least one dose of BIIB105 120 mg in either Part 1 or Part 2.
Data Included	All data from BIIB105 120 mg during Part 1 and Part 2. For those who initiated BIIB105 120 mg in Part 2, data from Part 1 are not included here	All data since first dose of BIIB105 60 mg, and before their first dose of escalation to 120 mg in Part 2.	All data since first dose of BIIB105 120 mg.

CONFIDENTIAL

The information contained herein may not be used, disclosed, or published without the written consent of Biogen MA Inc.

Table 5: Analysis Methods for Part 2 and Integrated Summary of Safety Data

Endpoints	Summary/Analyses	Part 2		Integrated Part 1 and Part 2		
		60 mg	120 mg	Pool BIIB105 120 mg DL (DL1, DL2)	Pool BIIB10 5 60 mg	Pool BIIB105 120 mg
Disposition	Accounting of participants	x	x	x		
Medical history	Summary	x	x			
Concomitant medications	Summary	x	x			
Adverse event	Overall summary AE by SOC and PT SAE by SOC and PT Adjusted incidence rate	x	x	x	x	x
CSF lab tests	Shift table Spaghetti plots Post-baseline evaluation of CSF WBC and CSF protein	x	x	x	x	x
Other lab tests	Descriptive analysis, shift table	x	x			
Vital Signs	Descriptive analysis	x	x			
ECG	Descriptive analysis, shift table	x	x			
Neurological Examination	Descriptive analysis	x	x			
PK	CSF concentration descriptive statistics	x		x		

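### CSF laboratory tests get no by-group summary of actual values or change from baseline, although the protocol requires one and neither SAP declares the departure

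*SAP*

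**What the plan says.** Protocol 13.3.1.2 defines the scope: "Laboratory data includes hematology, coagulation, blood chemistry, CSF assessments, and urinalysis, and will be summarized". It then sets the content: "Summary statistics for actual values and changes from baseline will be presented for quantitative laboratory data". Shift tables come in addition to that.

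Part 1 SAP 5.7.2 gives observed values, change and percent change for three panels only: "percentage change from baseline in laboratory values of hematology, blood chemistry, and coagulation will be summarized by treatment group and visit". For CSF it plans:

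- shifts: "For each hematology, blood chemistry, coagulation and CSF laboratory, the number and percentage of participants experiencing post-dosing shifts" to low or high;
- cut-offs: "Proportion of participants with CSF WBC values above 5, 10, and 20" × 10⁶/L, and protein above 2, 3 and 4 times the upper limit of normal (ULN);
- spaghetti plots by site, and listings with abnormal values flagged.

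Final SAP 5.7.2 names the same three panels. Its Table 5 gives CSF a row of its own (shift table, spaghetti plots, and "Post-baseline evaluation of CSF WBC and CSF protein"), while the row for other laboratory tests receives descriptive analysis.

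**The concern.** The drug is given into the CSF and the study's primary objective is safety and tolerability. CSF white cells and protein are the collected safety tests nearest to the site of administration. They are also the only laboratory set that Final SAP Table 5 carries into all three integrated pools. Protocol 3.2.3.1 reports CNS inflammatory changes, judged nonadverse, in one animal of the 41-week primate study.

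Yet no planned group table shows how far CSF values move, or when, at each dose. Shift and cut-off tables count participants who cross a line. They do not register a rise that stays within the normal range. For protein there is a further gap. In the shift table, "The number at risk for the shift to high is the number of participants whose baseline value is not high", so a participant who starts high enters no group table until the value passes 2 × ULN. The ULN itself may differ between sites, because the central laboratory handles the samples "except for urine pregnancy tests and CSF, which will be analyzed by a local laboratory".

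**Working it through.** **1. Text against text.**

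| Source | Panels given actual values and change from baseline |
|---|---|
| Protocol 13.3.1.2 | Quantitative laboratory data, CSF included |
| Part 1 SAP 5.7.2 | Hematology, blood chemistry, coagulation |
| Final SAP 5.7.2 and Table 5 | The same three panels; CSF row without descriptive analysis |

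Section 6 of the Part 1 SAP declares one change and Section 6 of the Final SAP declares two. All three concern time-to-event analyses.

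**2. Group sizes.** From Protocol 5.3.1:

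- 120 mg: 36 + 12 = 48.
- Placebo, Cohorts A to D1: 2 + 2 + 3 + 12 = 19, which reproduces the figure in the sample-size section.
- Pooled Placebo 1+2: 19 + 1 + 6 = 26.

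Both Part 1 schedules give 7 post-baseline CSF samples: Days 15, 29, 57, 85, 92, 130 and 175 for Cohorts A to C2, and Days 15, 29, 57, 85, 113, 141 and 169 for D1/D2 participants who enter Part 2.

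**3. Protein: what a change summary can resolve.** The documents give no CSF level, SD or ULN, so all of these are assumed. A two-sided 5% test serves only as a yardstick, since the plan tests no safety laboratory value. With within-person log SD *w*, the group difference in log ratio to baseline at one visit has SE = *w*√2 × √(1/48 + 1/26) = *w*√2 × 0.2435.

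- *w* = 0.15: SE = 0.0517. A 20% rise is ln 1.2 = 0.1823, so z = 3.53 and power ≈ Φ(3.53 − 1.96) = 94%.
- *w* = 0.20: SE = 0.0689, z = 2.65, power ≈ 75%.

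**4. Protein: simulated comparison with the planned tables.** Set A: baseline geometric mean 0.7–1.0 × ULN, between/within log SD 0.30/0.15 or 0.40/0.20, t test on the log ratio, 600 trials per scenario. Set B: median 40, ULN 45, between-person log SD 0.35, within-person 0.18–0.25, baseline-adjusted log protein, 1,500 trials per scenario. Fisher tests are used for the two counts.

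| True rise at 120 mg | Change at one visit | Any-visit shift to high | Any value > 2 × ULN |
|---|---|---|---|
| 15% (B) | 41–66% | 15–20% | 9–10% |
| 20% (A) | 73–94% | 20–47% | 0–18% |
| 25% (B) | 82–96% | 33–43% | 23–26% |
| 30% (A) | 94–100% | 39–79% | 0–42% |
| 50% (A) | about 100% | 71–98% | 7–91% |

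**5. Share outside the shift-to-high denominator.** This is 1 − Φ(ln(ULN/median) / √(between² + within²)).

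- Set B: ln(45/40) = 0.118, divided by 0.394 to 0.430, gives 38–39%.
- Median at 0.6 × ULN with SD 0.394: about 10%.
- Median at the ULN: 50%.

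The share therefore depends almost wholly on the assumed median.

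**6. White cells.** The ranking depends on the count model.

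- Poisson counts around a stable personal mean, baseline 1–2, rise of 1 cell: single-visit change signals in 39–68% of trials, the shift table (normal limit 5) in 18–57%.
- Mean 1 versus 2, change in log(count + 0.5), personal gamma shape 0.7–3, with and without extra visit-to-visit variation: change signals in 21–57%, any value above 5 in 29–70%. With the extra variation the cut-off did better in every scenario.
- Rise of 2 cells under the Poisson model: the shift table signals in 49–99%.

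**The case against.** General text in the Part 1 SAP could be read to cover CSF. Section 3.1 promises by-visit descriptive statistics for laboratory data, and 5.7.2 opens by saying that changes will be shown relative to baseline and then lists CSF among the parameters. This does not carry the point. The sentence that specifies the statistics names three panels, and Final SAP Table 5 confirms that CSF is handled apart.

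Other objections stand and limit the claim:

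- A reader might infer that a moderate CSF rise at 120 mg would probably be missed. The documents do not support that. The shift table works at 1 × ULN, counts any post-baseline visit including unscheduled ones, and is shown by dose level against placebo. All values are listed, and abnormalities judged clinically significant become adverse events.
- A reader might infer that change from baseline always beats a cut-off. For white cells it does not. Averaging log counts over all visits gave 76% against 51% for the above-5 cut in one scenario, but that is a different analysis from a by-visit change.
- The local-ULN argument applies to the shift flags and the protein multiples, not to the white-cell cut-offs, which are absolute counts.
- Participants high at baseline leave only the shift denominator. They stay in the cut-off proportions.
- Text directly after the white-cell cut-offs in Final SAP 5.7.2 is redacted, and that SAP says its analyses are simplified for an abbreviated report.

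**Conclusion.** The conflict with the protocol is real, undeclared and independent of any assumption: the protocol requires a summary for CSF that the SAP text does not provide. It is clearest in the Part 1 SAP. For the Final SAP it rests on the visible text and Table 5.

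The consequence is limited. What would be hard to see is the size and time course of CSF change by dose group, protein rises of about 15–25%, rises within the normal range, and protein rises below 2 × ULN in participants already high at baseline. A protein rise near 50% would usually show in the shift table, the 30% case is mixed, and no consistent gain is shown for white cells over the above-5 cut-off. Every sensitivity figure rests on assumed CSF levels, SDs and ULN. This should be corrected, but it does not show that the planned tables would hide a large CSF effect.

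**What to change.** In Part 1 SAP 5.7.2, add CSF white cells, red cells, protein and glucose to the descriptive statistics by visit and treatment group (observed value and change from baseline) and to the line plots. Placebo is pooled over two schedules, so group comparisons are cleanest at the shared post-baseline CSF days: 15, 29, 57 and 85.

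Add the same descriptive statistics to Final SAP 5.7.2 and to the CSF row of Table 5, or state in its Section 6 that the abbreviated report omits them. Keep the shift and cut-off tables.

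An optional addition, beyond what the protocol asks, is the geometric mean ratio to baseline for protein, 120 mg against Pooled Placebo 1+2, with a 95% CI.

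The cost is a line of SAP text and a few tables and plots from data already collected and listed. No new samples are needed.
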